##### **10.1.3 Revisions and Corrections**

All corrections to primary study documents will be initialed and dated. If computer-readable data is corrected by replacement of a data set, the replaced version of the data set will be retained in an archive. Corrections to electronic data will be stored in a tabular form; that is, for each data set within the master database, an auxiliary data set is retained that records each addition, deletion or correction to records in that data set. The collection of these auxiliary data sets represents an audit trail of corrections to the database. A single program uses the audit records to update the database as required.

##### **10.1.4 Archives**

In addition, to the standard system backup for PDMS for the clinical data of the protocol, the master database itself will be archived weekly to zip discs, which will be kept in a secure place. In addition, paper reports will be produced of all changes made to the data set. A paper listing of the data set will be produced periodically and kept off-site.

##### **10.1.5 Security**

Prior to registration, a registration checklist on-study form must be completed. It is added, along with the signed consent, to the individual subject's protocol research file. Each subject is assigned a unique study identification number, which will be used on all study forms and specimens. The study subjects' protocol research files and a coded list of subjects on the study will be kept in a key-locked filing cabinet in the department of Clinical Cancer Prevention. Confidentiality of the patients will be maintained and information kept on each patient will be made available only to identified investigators. Fields which could identify subjects, such as name, address, or social security number will not be stored electronically and will be stored as paper reports under lock and key at all times. All computer systems will be password-protected. Non-commercial software will not be

loaded onto the Intel-based computer dedicated to the data management. The redundant backups described above allow for quick restoration of data in the unlikely event that a security breach (or the more likely event of hardware failure) occurs.

## **10.2.0 Data Entry**

### **10.2.1 Clinical Data Entry**

Data will be entered into the PDMS database in case report forms after responses to all queries have been received. In case of missing data, a brief explanation is to be recorded as a comment.

### **10.2.2 Laboratory Data Entry**

Laboratory data are recorded on forms and later entered into the Microsoft -access electronic database. The sample identification number should allow only individuals who have access to the clinical data to trace the sample to a specific patient. The sample identification number is however coordinated to ensure that sample identifiers internal to the laboratory can be unambiguously traced to a specific patient by the principle investigator. All questions of sample identity will be resolved before laboratory data are merged into the master database.

## **10.3.0 Data analyses**

### **10.3.1 Hypotheses to be tested:**

NSAIDs downregulate GATA-6 expression to restore 15-Lox-1 expression that increases 13-S-HODE production, reduces PPAR-d expression, and thereby induce apoptosis in human colorectal tumors.

### **10.3.2 Predictor variables**

- a. Tissue disease status defined into one of two categories: normal-appearing mucosa, or polyp (tumor).
- b. Treatment status: pre- versus post- celecoxib treatment.

### **10.3.3 Outcome variables**

- A. Primary outcome variable: 13-S-HODE, 15-LOX-1 primary product, levels (measured by ELISA assay).
- B. Co-primary outcome variables: 15-LOX-1, PPAR-d, and GATA-6 levels (measured by western blotting and immunohistochemistry) and apoptosis (measured by TUNEL and casapse-3 immunohistochemistry).
- C. Secondary endpoint: PGE2 levels (measured by EIA) and COX-2 expression by immunohistochemistry and western blotting

### **10.3.4 Confounding variables**

Information regarding age, calcium, and folate supplement intake will be collected at the subject level and the effect of these variables will be assessed as potential confounders.

### **10.3.5 Statistical analysis:**

**(a)** Primary end point analyses: The patients in the study will be dichotomized into responders and non-responders. Responders will be defined as patients with at least a 25% reduction in their number of colorectal polyps. The primary analysis will be to compare the mean change in 13 S HODE values from baseline to post-treatment between the responders and non-responders. To account for the correlation of multiple tumors within a single patient, mixed models (PROC MIXED in SAS) will be used to perform this test.

**(b)** Analysis for primary and secondary endpoint: 13 S HODE levels will be correlated with the ratio of normal to cancer tissue levels of 15 LOX 1, GATA 6, and TUNEL and caspase 3 using Pearson and Spearman Correlation, as well as mixed models. Additionally, multivariate analyses will be applied to investigate the relationship between these measurements and confounding variables.

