### **10.3.6 Sample size justification**

In this study, we will measure 13-S-HODE levels in triplicate in 10 polyps taken at baseline and in 10 polyps taken after 6 months of treatment with celecoxib from each of 40 patients. As previously mentioned, these polyps will be selected independent of size so that there is no systematic bias induced by selecting larger polyps, for example. This sample size will allow us to have at least 80% power to detect a 25% increase in mean 13-S-HODE levels from baseline to 6 months (from 0.63 to 0.79 ng/g protein, for a mean difference of  $\Delta = 0.16$ ) using a paired *t* test with a two-sided significance level of 0.05, assuming that the standard deviation for the paired differences is  $\sigma = 0.355$ . These estimates are based on preliminary data from our laboratory on the 13-S-HODE levels of polyps, and the details of how we arrived at these values are given below. These calculations make the conservative assumption that there will be no correlation between the baseline and 6-month values. See the table below for details on the power calculations based on different values for the effect size,  $\Delta$ , and standard deviation,  $\sigma$ , which depends on the correlation between baseline and 6-month means from the same patient,  $\rho$ . If the correlation is  $\rho = 0.40$ , our power to detect a 25% increase in 13-S-HODE level from baseline to 6 months is 95%. With 40 patients and 10 polyps per patient, we have  $> 99.9\%$  power to detect a change in 13-S-HODE level of at least 50% (from 0.63 to 0.94 ng/g protein, irrespective of the value of  $\rho$ ).

**Table 1:** Power for paired *t* test with two-sided significance level of 0.05 to detect significant change in mean 13-S-HODE level from baseline to 6 months as a function of effect size,  $\Delta$ , and standard deviation,  $\sigma$ , which depends on the correlation between baseline and 6-month measurements,  $\rho$ .

Mean change in 13-S-HODE	Mean change from baseline to 6 mo ()	0	0.10	0.20	0.30	0.40	0.50

			0.355	0.337	0.318	0.297	0.275	0.251
25%	0.160	0.80	0.83	0.87	0.91	0.95	0.98	
50%	0.310	> 0.999	> 0.999	> 0.999	> 0.999	> 0.999	> 0.999	

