Here we describe in detail the assumptions we made to arrive at our choice of effect size and standard deviation for the power calculations. First, we assume that a subset of patients with FAP will respond to celecoxib and that others will not respond. We define patients as responders if they experience a 25% reduction in polyp count from baseline to 6 months. Second, we assume that nonresponders will experience no change in their mean 13-S-HODE levels from baseline to 6 months. Our preliminary data showed that the mean 13-S-HODE level in patients' polyps before celecoxib treatment is 0.63 ng/g, so we assume that this will be the mean value at both baseline and 6 months for the nonresponders. Third, we compute the power under two assumptions for the responders: that they will experience a 50% increase or a 100% increase (i.e., a doubling) of 13-S-HODE level from baseline to 6 months. Assuming a baseline mean 13-S-HODE value of 0.63 ng/g means that the mean 6-month value for responders would be 0.94 or 1.26 ng/g, respectively. In our preliminary data, the mean 13-S-HODE level for normal tissue was 3.35 ng/g, and the mean ratio of 13-S-HODE between normal tissue and polyps was 5.27. Fourth, we assume that roughly half of the patients will be responders. In the study by Steinbach et al (12), 53% of the patients had a > 25% reduction in polyp counts and would have been considered responders by our definition. In Specific Aim 2, we compare the 13-S-HODE levels in responders and nonresponders, but in this Specific Aim, our analysis focuses on testing whether the mean 13-S-HODE level in polyps changes from baseline to 6 months for all patients, irrespective of response to treatment. Thus, we compute the power for an overall 25% or 50% increase in 13-S-HODE (from 0.63 ng/g to 0.79 or 0.94 ng/g), which corresponds to no change in the half of patients that are nonresponders and a 50% or 100% increase, respectively, in the half that are responders. Fifth, we assume that the variance in the mean 13-S-HODE level for a given patient (averaging values for 10 polyps, with 13-S-HODE measured in triplicate) at both baseline and 6 months is  $s^2 = 0.063$ , which is estimated using a variance component analysis on the preliminary data. In this variance component analysis, we estimated the patient-to-patient variation to be  $s^2_{11} = 0.0563$ , the polyp-to-polyp variation to be  $s^2_{22} = 0.0520$  and the replicate-to-replicate variation to be  $s^2_{33} = 0.0629$ . Routine statistical calculations show that the variance of the mean 13-S-HODE level for a patient (averaging values for 10 polyps, with triplicate measurements per polyp) is  $s^2_{11} + s^2_{22}/10 + s^2_{33}/30 = 0.063$ . Sixth, we assume that the mean baseline and 6-month 13-S-HODE levels for a given patient will likely be correlated with each other. Routine statistical calculations, letting  $\rho$  represent this correlation, show that the standard deviation of the difference

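### Section 10.3.5(a) makes the responder comparison of 13-S-HODE change the primary analysis, but 10.3.6 gives power only for a paired test of overall change

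*Combined protocol and SAP*

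**What the plan says.** Section 10.3.5(a) splits patients by whether their polyp count fell by at least 25% and then says: "The primary analysis will be to compare the mean change in 13 S HODE values from baseline to post-treatment between the responders and non-responders". A mixed model is to be used because each patient contributes several polyps. Section 10.3.5(b) adds correlation, mixed-model and multivariate analyses; it begins "13 S HODE levels will be correlated with the ratio of normal to cancer tissue levels of 15 LOX 1, GATA 6". Neither part lists a test of the overall 13-S-HODE change in all patients.

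Section 10.3.6 claims "at least 80% power to detect a 25% increase in mean 13-S-HODE levels from baseline to 6 months", using a paired t test "with a two-sided significance level of 0.05, assuming that the standard deviation for the paired differences is" 0.355. It states the scope directly: "our analysis focuses on testing whether the mean 13-S-HODE level in polyps changes from baseline to 6 months for all patients", whatever their response. The responder contrast is put elsewhere: "In Specific Aim 2, we compare the 13-S-HODE levels in responders and nonresponders".

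Responder status enters the sizing only as a way to reach the overall effect. The plan says "Fourth, we assume that roughly half of the patients will be responders" and "we assume that nonresponders will experience no change in their mean 13-S-HODE levels from baseline to 6 months". Responders are assumed to rise by 50% (0.63 to 0.94 ng/g) or 100% (0.63 to 1.26 ng/g), which averages to an overall rise of 25% or 50%.

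**The concern.** The two sections point to different primary tests. They ask different questions: whether the change in 13-S-HODE tracks polyp response, and whether 13-S-HODE changes on average over 6 months. Section 1.0 has no numbered aims, so the reference to Specific Aim 2 does not rank them.

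The rest of the protocol does not settle it. The before-and-after objective in 1.0, the hypothesis in 10.3.1 and the pre/post predictor in 10.3.2 fit the overall test, and 10.3.2 does not list responder status. The target-validation rationale in 2.7.0 could support the responder test.

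Two things are at stake. A reader who takes 80% to 95% as the power of the primary analysis is reading another test's figure. And if the two tests disagree, either could be presented as the primary result.

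**Working it through.** **Inputs, all from 10.3.6 unless noted.** N = 40; two-sided alpha 0.05; overall change 0.16; variance of a patient's mean 13-S-HODE 0.063; SD of change = sqrt(2 × 0.063 × (1 − rho)), where rho is the correlation between a patient's baseline and 6-month means. Responders change by 0.94 − 0.63 = 0.31, non-responders by 0. About half respond, taken as 20/20. The plan's best guess for rho is 0.43.

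**Step 1: reproduce the plan's power.** For a paired t test the noncentrality is 0.16 / (SD / sqrt(40)) with 39 df. At rho = 0 this is 0.16 / (0.355 / 6.325) = 2.85, giving power 0.794. All six values in the 25% row of Table 1 reproduce to within a point (table below), so the published figures are those of the overall test.

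**Step 2: power of the named primary.** I use a two-sample t test on patient-level mean change as a stand-in for the mixed model. It assumes equal polyp numbers and equal SD of change in both groups. The noncentrality is 0.31 / (SD × sqrt(1/20 + 1/20)) with 38 df. At rho = 0 this is 0.31 / (0.355 × 0.316) = 2.76, giving power 0.768.

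| rho | SD of change | Table 1 (overall test) | Overall test, recomputed | Responder test, 20/20 |
|---|---|---|---|---|
| 0 | 0.355 | 0.80 | 0.79 | 0.77 |
| 0.10 | 0.337 | 0.83 | 0.83 | 0.81 |
| 0.20 | 0.317 | 0.87 | 0.87 | 0.85 |
| 0.30 | 0.297 | 0.91 | 0.91 | 0.90 |
| 0.40 | 0.275 | 0.95 | 0.95 | 0.93 |
| 0.43 | 0.268 | not given | 0.96 | 0.95 |
| 0.50 | 0.251 | 0.98 | 0.98 | 0.97 |

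The responder test is 1 to 3 points lower throughout. It reaches 0.80 from rho of about 0.08. In the plan's other scenario, where responders double (difference 0.63), its power exceeds 0.99 at rho = 0.

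**Step 3: dependence on the split.** The number of responders is known only after treatment. The splits below are my assumption, with the difference held at 0.31.

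| Responders / non-responders | rho = 0 | rho = 0.43 | 0.80 reached from rho of about |
|---|---|---|---|
| 20/20 | 0.77 | 0.95 | 0.08 |
| 12/28 | 0.69 | 0.90 | 0.23 |
| 10/30 | 0.64 | 0.87 | 0.31 |

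**Step 4: a condition on the overall test.** The formula for the SD of change has no separate term for responders and non-responders changing by different amounts. If 0.063 excludes that difference, the spread of changes at 20/20 is sqrt(0.126 + 0.25 × 0.31²) = sqrt(0.126 + 0.024) = 0.387 at rho = 0, not 0.355. Simulating the paired t test with a fixed 20/20 split (200,000 runs) gives power 0.71 at rho = 0 and 0.90 at rho = 0.43, against 0.80 (Table 1) and 0.96 (step 1). If the responder count is random with probability one half, the figures are 0.69 and 0.87. If 0.063 already includes the difference, Table 1 stands.

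**The case against.** The strongest reply is that little follows numerically. On the plan's own inputs the two tests differ by 1 to 3 points. The plan itself calls rho = 0 very conservative, and at its best guess of 0.43 the named primary has power 0.95. The half-and-half split is not arbitrary, since 10.3.6 cites an earlier FAP study in which 53% would have counted as responders. Even at 10/30, power at rho = 0.43 is 0.87. The document also mentions both tests, so nothing has been left out of the science. All of this stands, and it limits the point to which test is primary and which power figure belongs to it.

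A reader might go further and infer that the trial is underpowered. The documents do not support that: the 80% claim fails for the named primary only near rho = 0, and then narrowly. Powers well below 0.69 can be produced for the overall test, but only by combining a responder share that the plan does not assume with the unconfirmed variance reading in step 4. That is a question about Table 1's SD and does not bear on which test is primary.

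A reader might also infer that the responder contrast is the wrong choice of primary. That does not follow either. Under the step 4 reading it has more power at 20/20 and rho = 0 than the overall test (0.77 against 0.71), and the rationale in 2.7.0 can justify it.

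What the reply does not answer is the text itself. One section names a primary analysis, the next powers another, and no other section reconciles them.

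**Conclusion.** The point holds as an inconsistency that should be fixed. The 80% to 95% in 10.3.6 is the power of a test that 10.3.5 does not list, and the test that 10.3.5(a) calls primary has no stated power. By calculation the latter is 0.77 to 0.97 over rho 0 to 0.5, and 0.95 at rho = 0.43. These figures rest on a 20/20 split, a difference of 0.31, equal SDs in the two groups, and a t test on patient means in place of the mixed model. Forty patients are adequate for either test at the assumed split, so the sample size need not change on this account.

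The analysis of the co-primary markers and any multiplicity rule for them are separate matters, and this conclusion does not depend on them.

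**What to change.** Name one primary test, in the same words, in 10.3.5(a) and 10.3.6. There are two ways:

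- Make the overall baseline-to-6-month change in polyp 13-S-HODE primary and the responder contrast a key secondary analysis. This fits the objective in 1.0 and the hypothesis in 10.3.1. In that case, say whether 0.063 excludes responder/non-responder differences in change, and restate Table 1 if it does.
- Keep the responder contrast primary, and align the objective in 1.0 and the sizing text in 10.3.6 with it.

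Either way, give the power of the chosen test over rho 0 to 0.5, including 0.43, and over a range of responder fractions. Replace the Specific Aim wording with primary and secondary labels.

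The cost is wording in two sections and a revised power table, plus the objective under the second option. No new patients, visits or assays are needed, and both 13-S-HODE tests are kept.

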### **10.3.6 Sample size justification**

In this study, we will measure 13-S-HODE levels in triplicate in 10 polyps taken at baseline and in 10 polyps taken after 6 months of treatment with celecoxib from each of 40 patients. As previously mentioned, these polyps will be selected independent of size so that there is no systematic bias induced by selecting larger polyps, for example. This sample size will allow us to have at least 80% power to detect a 25% increase in mean 13-S-HODE levels from baseline to 6 months (from 0.63 to 0.79 ng/g protein, for a mean difference of  $\Delta = 0.16$ ) using a paired *t* test with a two-sided significance level of 0.05, assuming that the standard deviation for the paired differences is  $\sigma = 0.355$ . These estimates are based on preliminary data from our laboratory on the 13-S-HODE levels of polyps, and the details of how we arrived at these values are given below. These calculations make the conservative assumption that there will be no correlation between the baseline and 6-month values. See the table below for details on the power calculations based on different values for the effect size,  $\Delta$ , and standard deviation,  $\sigma$ , which depends on the correlation between baseline and 6-month means from the same patient,  $\rho$ . If the correlation is  $\rho = 0.40$ , our power to detect a 25% increase in 13-S-HODE level from baseline to 6 months is 95%. With 40 patients and 10 polyps per patient, we have  $> 99.9\%$  power to detect a change in 13-S-HODE level of at least 50% (from 0.63 to 0.94 ng/g protein, irrespective of the value of  $\rho$ ).

**Table 1:** Power for paired *t* test with two-sided significance level of 0.05 to detect significant change in mean 13-S-HODE level from baseline to 6 months as a function of effect size,  $\Delta$ , and standard deviation,  $\sigma$ , which depends on the correlation between baseline and 6-month measurements,  $\rho$ .

Mean change in 13-S-HODE	Mean change from baseline to 6 mo ()	0	0.10	0.20	0.30	0.40	0.50

			0.355	0.337	0.318	0.297	0.275	0.251
25%	0.160	0.80	0.83	0.87	0.91	0.95	0.98	
50%	0.310	> 0.999	> 0.999	> 0.999	> 0.999	> 0.999	> 0.999	

Here we describe in detail the assumptions we made to arrive at our choice of effect size and standard deviation for the power calculations. First, we assume that a subset of patients with FAP will respond to celecoxib and that others will not respond. We define patients as responders if they experience a 25% reduction in polyp count from baseline to 6 months. Second, we assume that nonresponders will experience no change in their mean 13-S-HODE levels from baseline to 6 months. Our preliminary data showed that the mean 13-S-HODE level in patients' polyps before celecoxib treatment is 0.63 ng/g, so we assume that this will be the mean value at both baseline and 6 months for the nonresponders. Third, we compute the power under two assumptions for the responders: that they will experience a 50% increase or a 100% increase (i.e., a doubling) of 13-S-HODE level from baseline to 6 months. Assuming a baseline mean 13-S-HODE value of 0.63 ng/g means that the mean 6-month value for responders would be 0.94 or 1.26 ng/g, respectively. In our preliminary data, the mean 13-S-HODE level for normal tissue was 3.35 ng/g, and the mean ratio of 13-S-HODE between normal tissue and polyps was 5.27. Fourth, we assume that roughly half of the patients will be responders. In the study by Steinbach et al (12), 53% of the patients had a > 25% reduction in polyp counts and would have been considered responders by our definition. In Specific Aim 2, we compare the 13-S-HODE levels in responders and nonresponders, but in this Specific Aim, our analysis focuses on testing whether the mean 13-S-HODE level in polyps changes from baseline to 6 months for all patients, irrespective of response to treatment. Thus, we compute the power for an overall 25% or 50% increase in 13-S-HODE (from 0.63 ng/g to 0.79 or 0.94 ng/g), which corresponds to no change in the half of patients that are nonresponders and a 50% or 100% increase, respectively, in the half that are responders. Fifth, we assume that the variance in the mean 13-S-HODE level for a given patient (averaging values for 10 polyps, with 13-S-HODE measured in triplicate) at both baseline and 6 months is  $s^2 = 0.063$ , which is estimated using a variance component analysis on the preliminary data. In this variance component analysis, we estimated the patient-to-patient variation to be  $s^2_{11} = 0.0563$ , the polyp-to-polyp variation to be  $s^2_{22} = 0.0520$  and the replicate-to-replicate variation to be  $s^2_{33} = 0.0629$ . Routine statistical calculations show that the variance of the mean 13-S-HODE level for a patient (averaging values for 10 polyps, with triplicate measurements per polyp) is  $s^2_{11} + s^2_{22}/10 + s^2_{33}/30 = 0.063$ . Sixth, we assume that the mean baseline and 6-month 13-S-HODE levels for a given patient will likely be correlated with each other. Routine statistical calculations, letting  $\rho$  represent this correlation, show that the standard deviation of the difference

between the mean 13-S-HODE levels at baseline and 6 months is given by  $\sigma = \sqrt{2s^2(1-\rho)}$ . Since we do not have pretreatment and posttreatment preliminary data, we do not know what  $\rho$  should be, so we compute the power for values of  $\rho$  from 0 to 0.50 in increments of 0.10. Our best guess is that  $\rho$  should be close to the intraclass correlation between polyps within the same patient, which is given by  $s^2_{11}/(s^2_{11} + s^2_{22} + s^2_{33}/3) = 0.43$ . A value of  $\rho = 0$  is very conservative because we expect that there should be some positive correlation between the baseline and 6-month values.

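### The power table leaves out the variance created by the plan's own responder/non-responder mixture: the 80% claim is about 71–72%, and the claim of more than 99.9% at any correlation fails.

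*Combined protocol and SAP*

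**What the plan says.** All of this is in section 10.3.6 of the combined protocol and SAP. Levels are measured in ten polyps at baseline and ten "after 6 months of treatment with celecoxib from each of 40 patients". The headline claim is "at least 80% power to detect a 25% increase in mean 13-S-HODE levels from baseline to 6 months". In absolute terms that is Δ = 0.16 on a baseline of 0.63 ng/g. The calculation is for a paired t test at the two-sided 5% level with σ = 0.355, the value at ρ = 0. Power is given as 95% at ρ = 0.40, and as above 99.9% for a 50% rise ("from 0.63 to 0.94 ng/g protein, irrespective of the value of" ρ).

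The section then explains the effect size. Roughly half the patients are expected to respond. Non-responders stay at 0.63 ng/g and responders rise by 50% or 100%. The overall 25% or 50% rise therefore "corresponds to no change in the half of patients that are nonresponders and a 50% or 100% increase, respectively, in the half" who respond. The test covers all patients, whatever their response.

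For the spread, "we assume that the variance in the mean 13-S-HODE level for a given patient" is 0.063 at both time points, built from patient, polyp and replicate components in preliminary data. The standard deviation of the difference is σ = √(2s²(1−ρ)). Both rows of Table 1 use the same σ.

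**The concern.** The mixture sets the mean change but is ignored in the standard deviation. If half the patients do not change and half rise by D, true change differs between patients, and that difference belongs in the variance of the paired differences. Leaving it out makes σ too small and power too high. It also explains why both rows share one σ, although doubling the responders' change must widen the spread.

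At stake are the figures that support 40 patients: the 80% presented as a cautious floor, the 95% at ρ = 0.40, and the statement that power for a 50% rise exceeds 99.9% at any correlation. A reader would take these as following from the stated assumptions, and they do not.

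**Working it through.** **Inputs, all from section 10.3.6.** n = 40 (39 df); two-sided α = 0.05; s² = 0.063; responder share p = 0.5; non-responders' change 0; responders' change D = 0.315 (50% of 0.63) or 0.63 (100%). The mean change pD is 0.1575 or 0.315; the plan prints 0.16 and 0.31. Dropouts are replaced (section 7.12.0), so n stays at 40.

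**Step 1: reproduce the plan.** Power comes from the noncentral t with noncentrality Δ√40/σ and σ = √(2 × 0.063 × (1−ρ)). At ρ = 0, σ = √0.126 = 0.355 and the noncentrality is 0.16 × 6.325/0.355 = 2.85, giving power 0.794. The full 25% row is 0.794, 0.834, 0.874, 0.914, 0.948, 0.976, against the printed 0.80, 0.83, 0.87, 0.91, 0.95, 0.98. The 50% row is 0.9997 or higher. The table is right for its σ.

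**Step 2: add the mixture variance.** A change of 0 with probability 1−p and D with probability p has variance p(1−p)D²:

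- 50% rise in responders: 0.25 × 0.315² = 0.0248
- 100% rise in responders: 0.25 × 0.63² = 0.0992

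So σ = √(2s²(1−ρ) + p(1−p)D²). At ρ = 0 this is √(0.126 + 0.0248) = 0.388 and √(0.126 + 0.0992) = 0.475.

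**Step 3: recompute Table 1.** Two versions of the 25% row separate the effect of rounding from that of the mixture.

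| ρ | 25% row, printed | Corrected, Δ = 0.16, D = 0.32 | Corrected, Δ = 0.1575, D = 0.315 | 50% row, printed | Corrected, Δ = 0.31, D = 0.63 | Corrected, Δ = 0.315, D = 0.63 |
|---|---|---|---|---|---|---|
| 0 | 0.80 | 0.72 | 0.71 | > 0.999 | 0.981 | 0.984 |
| 0.10 | 0.83 | 0.75 | 0.74 | > 0.999 | 0.986 | 0.988 |
| 0.20 | 0.87 | 0.79 | 0.78 | > 0.999 | 0.990 | 0.991 |
| 0.30 | 0.91 | 0.83 | 0.82 | > 0.999 | 0.993 | 0.994 |
| 0.40 | 0.95 | 0.87 | 0.87 | > 0.999 | 0.996 | 0.996 |
| 0.50 | 0.98 | 0.91 | 0.91 | > 0.999 | 0.997 | 0.998 |

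**Step 4: simulate, because a mixture is not normal.** With each patient a responder with probability one half and D = 0.315, power is 0.71 at ρ = 0 and 0.87 at ρ = 0.40. With D = 0.63 it is 0.984 at ρ = 0. With exactly 20 responders and 20 non-responders, the values are 0.72, 0.90 and 0.997.

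**Step 5: sample size.** At ρ = 0 in the 25% row, 80% power takes 49 patients (Δ = 0.16, D = 0.32) or 50 (Δ = 0.1575, D = 0.315).

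**Step 6: the scale of ρ.** The best guess of 0.43 is the correlation between single polyps, 0.0563/(0.0563 + 0.0520 + 0.0629/3). The formula for σ concerns ten-polyp means. Their variance is 0.0563 + 0.0520/10 + 0.0629/30 = 0.0636, so the same components allow ρ up to 0.0563/0.0636 = 0.885 if patient effects are fully stable over six months.

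**The case against.** Five points can be made for the plan.

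- **ρ = 0 is deliberately pessimistic.** The plan says so. At its best guess of 0.43, corrected power is 0.88–0.89, and near the 0.885 ceiling it would be about 0.998. This stands, and it is why enrolment need not change. But the plan offers 80% as its ρ = 0 figure, and that figure is wrong.
- **Part of the fall is rounding.** Using 0.1575 instead of 0.16 lowers power at ρ = 0 from 0.794 to 0.781 with no mixture term. Like for like, the mixture costs 7.5 to 8 points. This stands, and it moves the corrected value by only about one point.
- **The half could mean exactly 20 of 40.** In simulation, that split restores more than 0.999 in the 50% row from ρ = 0.20 upward, and takes the 25% row past 0.80 from ρ = 0.20. The printed values still fail at ρ = 0. Because response is observed after treatment and the share is only approximate, random status is the natural reading.
- **s² = 0.063 at six months might already include the mixture.** It cannot for the 100% rise, where the mixture alone adds 0.099. For the 50% rise, other variance would have to shrink on treatment, which the plan does not say.
- **Section 10.3.5(a) names a different primary analysis,** the comparison of responders with non-responders. There the gap between the groups is the signal, so this term would not enter its error variance. That is true, but section 10.3.6 gives no power for that comparison, and Table 1 is the stated basis for 40 patients.

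**Conclusion.** The concern holds. Under the plan's own assumptions, power for the all-patient paired t test at ρ = 0 is 0.71–0.72, not at least 0.80. At ρ = 0.40 it is 0.87, not 0.95. The 50% row lies between about 0.98 and 0.998, so the claim of more than 99.9% at any ρ is false, though that shortfall has little practical weight. With responder status random, every cell of Table 1 is overstated; with an exact 20/20 split, the upper-ρ cells of the 50% row survive.

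The result assumes a responder share of 0.5, a common change D in all responders, and s² = 0.063 otherwise unchanged at six months. If the rise were instead proportional to each patient's own level, power would be lower still, about 0.61 and 0.95 at ρ = 0 for the two rows. Corrected power reaches 80% somewhere between ρ = 0.20 and 0.30, below the plan's best guess. The table needs restating; the sample size does not need to change on this ground.

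**What to change.** In section 10.3.6:

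1. Compute σ as √(2s²(1−ρ) + p(1−p)D²), with p = 0.5 and D = 0.315 or 0.63. Each row of Table 1 then has its own σ.
2. Replace the statements of at least 80%, of 95% at ρ = 0.40, and of more than 99.9% whatever ρ is, with the recomputed values. State that responder status is treated as random.
3. Quote ρ for ten-polyp means, the scale to which the formula applies, and extend the tabulated range to match.

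Keep 40 patients. The cost is a restated table and a few sentences, and a less favourable power statement at low ρ. Enrolment and procedures are unaffected.
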